8.1 Primary Efficacy Analysis

Incisal Bite Force (lbs): Area over Baseline (AOB₀₋₁₂)

The Area Over Baseline (AOB) over 12 hours for the incisal bite force (lbs) (denoted by AOB_{0-12}) is the primary efficacy variable.

To calculate this variable first the Area Under the Curve (AUC) is calculated from 0 to 12 hours (AUC₀₋₁₂) using the trapezoidal method. AOB₀₋₁₂ will be calculated as (AUC₀₋₁₂)/12 minus baseline bite force (lbs). This transformation will return the measurement to the same scale as the original observations whilst also looking at the average amount of improved force over time by subtracting the baseline value (AOB: Area Over Baseline). Higher values of AOB demonstrate a stronger bite force over time than lower values.

Document Name	Statistical Analysis Plan for Study 206233.docx		
Туре	Version	Document Identifier	Effective Date
eldo clinical doc	1.0; CURRENT; Most-Recent; Effective	090032d580d17d34	27-Mar-2017 09:54:18
Reason For Issue	Auto Issue		

Missing readings will be ignored and interpolation will be made between pre and post the missing values, if necessary. In the case of more than one missing value or if the 12 hour value or the baseline value is missing, the AOB will be set to missing.

An analysis of covariance (ANCOVA) model will be used with AOB values as the response, with fixed effect factors for treatment group, period and subject-level baseline, period level baseline minus subject-level baseline as covariates. Subject will be included as a random effect.

From the above model, treatment differences between groups, (each of the two adhesives versus no adhesive), 95% confidence intervals and p-values, will be provided. The confidence intervals and p-values will be adjusted using the Dunnett's method so that the overall confidence level for the two confidence intervals is maintained at 95% and the two treatment comparisons can be performed with an overall 5% significance level.

8.2 Secondary Efficacy Analysis

Incisal Bite Force (lbs): Area over Baseline (AOB₀₋₁₂)

From the ANCOVA model described above, treatment difference for each of the two test adhesives versus Super Poligrip® Free and with each other will be provided along with 95% confidence intervals and p-values. All tests will be conducted at the two sided 5% significance level. If non-parametric analysis is performed for the primary efficacy variable then these secondary comparisons will be performed in a similar way as the primary comparisons.

8.3 Exploratory/Other Efficacy Analysis

Incisal Bite Force (lbs): Area over Baseline ($AOB_{0-0.5}$, AOB_{0-1} , AOB_{0-3} , AOB_{0-6} , AOB_{0-9})

Other efficacy bite-force efficacy variables analysed will be bite force AOBs over 0.5, 1, 3, 6 and 9 hours respectively. Each of these variables will be analysed using a similar ANCOVA model as described above for the primary efficacy variable.

From this model, treatment difference between each test adhesive versus Super Poligrip® Free, the treatment difference between each test adhesive versus no adhesive, 95% confidence intervals and p-values, will be provided. All significance tests will be conducted at the two sided 5% significance level.

Document Name	Statistical Analysis Plan for Study 206233.docx		
Туре	Version	Document Identifier	Effective Date
eldo clinical doc	1.0; CURRENT; Most-Recent; Effective	090032d580d17d34	27-Mar-2017 09:54:18
Reason For Issue	Auto Issue		

The data from the questionnaires and the denture adhesive weights will be listed and tabulated using descriptive statistics.

9 Safety Analysis

The safety profile of the study treatments will be assessed with respect to adverse events (AEs) and incidents. Oral soft tissue (OST) abnormalities are included as AEs if they appear or worsen after the initial assessment.

All safety data will be reported for the Safety population as per actual treatment received. All subjects screened will be included in the list of AEs.

All AEs will be reviewed by the Clinical Research Director or Designee prior to database freeze and will be coded using the Medical Dictionary for Regulatory Activities (MedDRA). During this review stage, AEs will be further categorized as oral or non-oral.

AEs will be regarded as treatment emergent if they occur on or after the date and time of the pre-treatment OST exam at the randomisation visit. All other AEs prior to this will be considered non-treatment emergent. AEs that occur during inter-test day washout are assigned to the last treatment received.

The following summary tables and listings will be presented by treatment group.

- Table of treatment emergent AEs by Oral/Non-Oral and Preferred Term
- Table of treatment emergent AEs by SOC and Preferred Term
- Table of Treatment emergent treatment related AEs by Oral/Non-Oral and Preferred Term
- Listing of all AEs (including Non-treatment emergent from All Subjects).
- Listing of serious AEs. (if there are none a null listing will be produced, if there are >5 treatment emergent SAEs a table will be produced by SOC and PT)
- Table of Non Serious treatment emergent AEs by SOC and Preferred Term.
 (only produced if there are > 5 SAEs)
- Listing of incidents (if there are none a null listing will be produced)

Document Name	Statistical Analysis Plan for Study 206233.docx		
Туре	Version	Document Identifier	Effective Date
eldo clinical doc	1.0; CURRENT; Most-Recent; Effective	090032d580d17d34	27-Mar-2017 09:54:18
Reason For Issue	Auto Issue		

No inferential analyses will be performed to compare treatments with respect to safety.

10 Interim Analysis

No interim analysis is planned for this study.

11 Topline Summary

The following outputs will be produced for the topline report.

Datasets/Tables	Description
Datasets	STAT1, STAT2
Tables	Table 9.1.1 – Subject Disposition
	Table 9.1.3 – Protocol Violations Leading To Exclusion From Per Protocol Analysis – ITT Population
	Table 9.3.1 – Summary of Bite Force (lbs) by Time – ITT Population
	Table 9.3.2.1 – Summary of AOB by Time – ITT Population
	Table 9.3.2.2 – Summary of AOB (0-12 Hours) – PP Population
	Table 9.4.4 – Listing Of All Adverse Events – All Subjects

The following table will be produced in .rtf format for input into the topline report:

Document Name	Statistical Analysis Plan for Study 206233.docx		
Туре	Version	Document Identifier	Effective Date
eldo clinical doc	1.0; CURRENT; Most-Recent; Effective	090032d580d17d34	27-Mar-2017 09:54:18
Reason For Issue	Auto Issue		

Table 1: Statistical Analysis of Between Treatment Group AOB over 12 hours (ITT Population)

Parameter	Time Point	Treatment Comparison	Difference	Lower CI	Upper CI	P-value
AOB	0-12 hours	Super Poligrip Free vs. No Adhesive	X.XX	X.XX	x.xx	x.xxxx
		Test Adhesive 1 vs. No Adhesive	X.XX	X.XX	X.XX	x.xxxx
		Test Adhesive 2 vs. No Adhesive	X.XX	X.XX	x.xx	x.xxxx
		Test Adhesive 1 vs. Super Poligrip Free	X.XX	x.xx	x.xx	x.xxxx
		Test Adhesive 2 vs. Super Poligrip Free	X.XX	X.XX	X.XX	x.xxxx
		Test Adhesive 1 vs. Test Adhesive 2	x.xx	X.XX	X.XX	x.xxxx

Positive control adhesive: Super Poligrip Free Adhesive Cream (USA); Test Adhesive 1: CC Test Adhesive 2: CC No adhesive [1] From ANCOVA with period and treatment as fixed effects, subject as random effect, and subject-level and period-level pre treatment baseline

bite force (parameterized as period-level minus subject-level) as covariates.

A similar table titled "Table 2: Statistical Analysis of Between Treatment Group AOB over 12 hours (PP Population)" using the PP population will be produced in the .rtf format for the topline report if it is determined at the Blinded Data Review that a Per Protocol analysis will be performed.

[figure not shown]
The following figure will be produced in .rtf format for input into the topline report:

^[2] Difference is first-named treatment minus second-named treatment such that a positive difference favors the first named treatment.

Document Name	Statistical Analysis Plan for Study 206233.docx		
Туре	Version	Document Identifier	Effective Date
eldo clinical doc	1.0; CURRENT; Most-Recent; Effective	090032d580d17d34	27-Mar-2017 09:54:18
Reason For Issue	Auto Issue		

Figure 1: Bite force (lbs) value over time by treatment group (ITT Population)

12 Changes to Planned Analysis

The analyses for efficacy has been re-organised to match the primary, secondary and other objectives.

13 References

None.

Document Name	Statistical Analysis Plan for Study 206233.docx		
Туре	Version	Document Identifier	Effective Date
eldo clinical doc	1.0° CURRENT: Most-Recent: Effective	090032d580d17d34	27-Mar-2017 09:54:18
Reason For Issue	Auto Issue		

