5.2. Dose Schedule

The denture adhesives will be applied by the Site Study Staff to a clean and dry upper complete denture following the pre-treatment baseline bite force measurement in accordance with the product Application Instructions (Appendix V & VI).

For adhesive test arms: A total of 1±0.05 gram (weighed) of denture adhesive will be applied to the dry maxillary denture in a pattern consistent with the product label and application instructions (Appendix V & VI). For all subjects in all arms: Super Poligrip® Free denture adhesive cream will be applied to the dry mandibular denture (if applicable) in a pattern consistent with the instructions on the product label.

Clean and dry upper complete dentures will be weighed and their masses recorded prior to and immediately following adhesive application for all products. The masses of the adhesives used will be calculated as the difference in the recorded masses preand post-adhesive application.

All application of denture adhesive should be made in an area not accessible by the examiner performing the bite force and OST (safety) assessment in order to ensure that the examiners remain blind. The denture will then be returned to the subject who should reposition the denture in their mouth. For subjects on the "no adhesive" treatment visit, the denture should be cleaned and dried as above, and then refitted by the subject, no weighing of the denture is necessary.

As stabilisation of the lower denture is necessary for accurate Bite Force measurements to be performed, reapplication of denture adhesive (to the lower denture only) may be performed up to a maximum of 2 times is acceptable on any given test day provided that; (1) the investigator deems it necessary for Bite Force measurements (2) the subject has been compliant with the protocol and has not actively washed the adhesive out.

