6.1.11. Mandibular Denture Stabilisation

Prior to all bite force measures, if deemed necessary at the discretion of the Investigator in order to ensure accuracy of bite force measures, any lower denture (partial or complete) will be fully stabilized by the investigator using the positive control denture adhesive (Super Poligrip® Free Adhesive Cream). This will be completed, when necessary, for all screening, practice, training and test bite force measurements.

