9.3.5. Safety Analysis(es)

Safety will be assessed based on any oral AEs (this includes those that are identified as Treatment Emergent OST abnormalities and spontaneously reported oral AEs). All AEs will be coded using the Medical Dictionary for Regulatory Activities (MedDRA). AEs will be categorized as oral and non-oral by the clinical research director or designee prior to database lock. AEs will be deemed to be TE if they occur after the first supervised use of the randomized treatment. No formal statistical analyses of AEs will be performed. A list of incidents will also be included as part of the safety analyses.

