post bite force phase	12 hours' use

3 Study Design

Overall Design

This single centre, randomized, crossover, proof-of-principle study will be a randomized four treatment, examiner blind [to the examiner performing the bite force & oral soft tissue (OST) examinations] design in subjects with well made and moderately well-fitting maxillary complete dentures. Informed consent will be obtained from participants before the implementation of any study procedure.

At the Screening Visit, subjects will be screened for eligibility and ability to perform the bite force manoeuvre according to stated inclusion/exclusion criteria. On the test day visit, subjects will report to the study site without adhesive placed in their dentures. Dentures will be removed and cleaned. An OST examination will be performed before the lower denture (if applicable) is secured using Super Poligrip[®] Flavour Free denture adhesive, whilst the upper denture is removed, and the pretreatment baseline incisal bite force measurements will be obtained (both practice bites and qualifying test bite). To maintain blinding, subjects must not disclose to the examiner if they are wearing adhesive or no adhesive. Subjects meeting all the inclusion criteria with no exclusions will then be randomized at Visit 2.

On each test day (Visits 2-5) subjects will undergo an OST examination and have their dentures cleaned. Denture adhesive treatment (or no treatment as per the randomization schedule) will then be applied by a member of study staff (ideally the same member of staff throughout the study) as per the application instructions, and the dentures worn by the subject. Incisal bite force measurements will be made at 0.5, 1, 3, 6, 9 and 12 hours after the dentures are placed in the mouth. After 0.5 hours assessment the subjects will be asked to complete questions about product ooze (Appendix II). The questions will be completed by the subjects themselves and these responses will then be given to study site staff to transfer to the eCRF.

Immediately following the last (12 hour) incisal bite force measurement, subjects will be asked to complete a short questionnaire relating to the after-taste and texture of the

Document Name	Statistical Analysis Plan for Study 206233.docx		
Туре	Version	Document Identifier	Effective Date
eldo clinical doc	1.0; CURRENT; Most-Recent; Effective	090032d580d17d34	27-Mar-2017 09:54:18
Reason For Issue	Auto Issue		

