- Mandibular denture stabilization (with adhesive, if deemed to be necessary to ensure accurate bite force measures; at the discretion of the Investigator)
- Three incisal bite force readings with no adhesive on the upper denture (for practice)
- Incisal bite force with no adhesive on the upper denture (pre-treatment "baseline")
- Subject eligibility
- Adverse events and incident reporting (assessed pre bite force measurement)
- Continued eligibility
- Randomisation (Test/Treatment day 1 only)
- Weigh maxillary denture prior to adhesive placement
- Product application by site staff to maxillary denture (or no adhesive for the no adhesive negative control)
- Weigh maxillary denture immediately following adhesive placement (record weight difference i.e. weight of adhesive used to ensure correct dose applied)
- Dentures of subjects randomized to a denture adhesive shall be weighed before & after adhesive application
- Upper denture insertion by subject
- Incisal bite force measurements (at 0.5 hours prior to product ooze questionnaire (Appendix II), followed by 1, 3, 6, 9 & 12 hours post adhesive application)
- Subject evaluation questionnaire (product ooze) 0.5 hours post adhesive application (Appendix II)
- Subject sensory questionnaire (flavour, texture and extrusion of the adhesive from the tube; Appendix III) immediately following the last (12 hr) bite force measure whilst upper denture still retained in the mouth
- Removal of denture from the mouth by the subject
- Denture adhesive retention questionnaire completed by Examiner/ site staff
- Removal of excess adhesive from the mouth by the subject facilitated by site study staff as and where necessary
- Subject denture removal questionnaire (Appendix IV) immediately following 12 hour post adhesive application bite force measure, completion of subject sensory questionnaire and subsequent removal of the upper denture
- Study Staff to check denture removal questionnaire completion to ensure that
 any potential AEs which may have been noted in the questionnaire free text is
 reviewed and captured in the eCRF before the subject leaves the site

Document Name	Statistical Analysis Plan for Study 206233.docx		
Туре	Version	Document Identifier	Effective Date
eldo clinical doc	1.0; CURRENT; Most-Recent; Effective	090032d580d17d34	27-Mar-2017 09:54:18
Reason For Issue	Auto Issue		

- Post-treatment OST by a blinded examiner
- · Dentures cleaned and returned to subject

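### The SAP starts the treatment-emergent period at the Visit 2 pre-treatment oral soft tissue exam, earlier than the protocol does; the change is not declared, and no written rule gives pre-application events a treatment column

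*SAP*

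**What the plan says.** The two documents define treatment-emergent (TE) events differently.

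- Protocol 9.3.5: "AEs will be deemed to be TE if they occur after the first supervised use of the randomized treatment".
- SAP section 9 (Safety Analysis): AEs are "regarded as treatment emergent if they occur on or after the date and time of the pre-treatment OST exam at the randomisation visit". Anything earlier is non-treatment-emergent.

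The randomisation visit is Visit 2; SAP section 3 states "Subjects meeting all the inclusion criteria with no exclusions will then be randomized at Visit 2".

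SAP section 9 reports safety data by the treatment actually received and presents the TE tables by treatment group. It gives one rule for assigning an AE to a treatment: events in the washout between test days go to the last treatment received. SAP Appendix 2 fixes four treatment labels for all outputs (Test Adhesive 1, Test Adhesive 2, Super Poligrip Free, No Adhesive) and has no pre-treatment label.

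SAP section 12, which records departures from the planned analysis, contains one sentence: "The analyses for efficacy has been re-organised to match the primary, secondary and other objectives". It says nothing about safety.

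**The concern.** A treatment-emergent table is meant to show what happened once subjects were exposed to the randomized products. If the window opens before the first product is applied, events from the study procedures, or from the adhesive on the lower denture, enter that table. They then have to sit somewhere in a layout whose only headings are the four treatments. The programmer must either put the event under a product not yet applied or make up a rule after the data are in. The study record would also hold two definitions of the same term, with nothing to tell a reader of the report that the SAP had replaced the protocol's.

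**Working it through.** No calculation applies to the main point. The check sets the two definitions against the order of events at Visit 2.

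**Step 1. What lies between the two starting points.** The screening list in SAP section 3 is said to be in order, but the list for Visits 2 to 5 is not, so the order is better taken from the narrative and Protocol 5.2.

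- SAP section 3, Overall Design: "An OST examination will be performed before the lower denture (if applicable) is secured". So the exam comes before lower-denture stabilisation.
- Protocol 6.1.11: where the investigator judges it necessary, "any lower denture (partial or complete) will be fully stabilized by the investigator using the positive control denture adhesive". This happens before all bite force measures.
- SAP section 3, Visits 2 to 5: "Three incisal bite force readings with no adhesive on the upper denture (for practice"), then one baseline bite, also without adhesive on the upper denture. That is 3 + 1 = 4 bites.
- SAP section 3, Overall Design: randomisation at Visit 2 comes after these measurements.
- Protocol 5.2: the product goes on the upper denture "following the pre-treatment baseline bite force measurement".

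The interval is therefore not empty. AEs are also collected in it: the Visits 2 to 5 list has an AE check between the baseline bite and randomisation.

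**Step 2. Classify Visit 2 events under each rule.**

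| Event at Visit 2 | Protocol 9.3.5 | SAP section 9 |
|---|---|---|
| Oral soft tissue abnormality new since screening, dated to the pre-treatment exam | Not TE | TE |
| Event after lower-denture stabilisation, before application | Not TE | TE |
| Event after one of the four no-adhesive bites | Not TE | TE |
| Event after the upper denture is re-inserted | TE | TE |

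The first row reads the initial assessment in SAP section 9 as the screening exam. This agrees with Protocol 6.1.7, which collects AEs from that exam.

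**Step 3. Look for a rule that assigns the column.** The washout rule needs an earlier treatment, and at Visit 2 before application there is none. The rule on treatment received does not say how an event that precedes all treatment is placed. The four labels in Appendix 2 include no pre-treatment category. No sentence in either document assigns the event.

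A smaller gap exists at Visits 3 to 5. The programming note to Table 9.1.2 ends washout the day before the next dose. If that definition also governs section 9, events on the test day before application fall outside the washout rule too, although there a last treatment exists to assign them to.

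**Step 4. Look for a declaration.** SAP section 12 covers efficacy only.

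**Step 5. Which outputs are touched.** Tables 9.4.1 and 9.4.2 directly; Table 9.4.3 only if such an event is judged treatment related; Table 9.4.6 only if there are more than 5 SAEs. The listing of all AEs is unaffected, because it includes non-treatment-emergent events from all screened subjects.

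**The case against.** The best case for the SAP is that its start may be the better one. It is a single timed point shared by all four arms, and the schedule footnote makes the test-day exam the pre-treatment baseline, against which later findings are naturally read. It is also the more inclusive choice for safety: a Visit 2 reaction to the lower-denture adhesive, which is the positive control product, would drop out of the TE tables under the protocol's rule. All of this stands as a reason to choose the earlier start. It does not declare the choice or settle the column. Protocol 9.3 lets the SAP add detail, but moving the start of the period is a change to a stated rule.

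Three stronger readings are tempting, and the documents do not support them.

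- *Such events can have no valid column.* In Protocol 9.2.1, analysis by treatment received stands in contrast to analysis as randomized; it need not mean received before onset. Every subject in the safety population has received at least one treatment, so placing the event under the period 1 treatment is possible. The AE tables also use standard shells that are not shown. What can be said is that no written rule assigns a column.
- *The protocol's start is undefined when period 1 is no adhesive.* It is not spelled out, but it can be inferred: Protocol 5.2 has the subject refit the cleaned denture in that arm, which is the matching step.
- *All of the approximately 21 randomized subjects are misclassified.* All of them pass through the interval, but that only restates the two definitions. It counts subjects, not events.

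**Conclusion.** The point holds as a minor inconsistency. SAP section 9 states a TE start that contradicts Protocol 9.3.5, the change is undeclared, and followed as written it puts events from before any randomized treatment into Tables 9.4.1 and 9.4.2 with no rule for their column.

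The number of events involved cannot be calculated, since neither document gives an AE rate; the exposure is one part-visit interval per subject. No safety comparison is inferential, every AE is listed whether TE or not, and the efficacy analyses are unaffected. The conclusion rests on the Visit 2 order given in SAP section 3 and Protocol 5.2, and on there being no assignment rule in the standard shells, which cannot be seen.

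**What to change.** Settle on one TE start before database freeze. Either option is acceptable.

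- **(a) Align SAP section 9 with Protocol 9.3.5.** Take re-insertion of the upper denture at Visit 2 as time zero in all four arms, including no adhesive; SAP section 3 already times bite force from placement of the dentures. List earlier Visit 2 events as non-treatment-emergent. This needs a Visit 2 placement time. The documents do not say that one is recorded, but the time-window review in SAP 5.1 already needs a time zero for each test day. Reactions to the lower-denture adhesive before application leave the TE tables, though they stay in the AE listing.
- **(b) Keep the exam as the start.** Declare in SAP section 12 that it replaces the protocol's definition, and show Visit 2 pre-application events in a separate column headed *before first treatment*, not under a product not yet applied. This adds one table column.

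Under either option, one further sentence can state that pre-application events at Visits 3 to 5 go to the last treatment received. The whole change is a few sentences in SAP section 9, plus one in section 12 under option (b), with no new assessment of subjects.
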